**Table 14.1.2.3**  
**Study Discontinuation by Time Period and by Region**  
**Safety Population**

Country		AD (N= )	bvFTD (N= )	All Subjects (N= )
Country 1	Study Discontinuation	n (%)	n (%)	n (%)
	Study Discontinuation on Day 1	n (%)	n (%)	n (%)
	Reason 1	n (%)	n (%)	n (%)
	Reason 2	n (%)	n (%)	n (%)
	...			
	Study Discontinuation During Days 2-	n (%)	n (%)	n (%)
	Reason 1	n (%)	n (%)	n (%)
	Reason 2	n (%)	n (%)	n (%)
	...			
	...			
	Repeat for other period categories			
	...			
...				

Note: Percentages are based on the number of subjects in the Safety Population.

**Table 14.1.3.1  
Protocol Deviations  
Safety Population**

	AD (N= )	bvFTD (N= )	All Subjects (N= )
All Deviations Types	n (%)	n (%)	n (%)
Informed consent	n (%)	n (%)	n (%)
Safety	n (%)	n (%)	n (%)
IP / Treatment Deviation	n (%)	n (%)	n (%)
Other Deviations	n (%)	n (%)	n (%)

Note: IP = investigational product

path\t\_program.sas date time

**Table 14.1.3.2**  
**Protocol Deviations by Critical, Major and Minor Categories**  
**Safety Population**

	AD (N= )	bvFTD (N= )	All Subjects (N= )
Critical Deviation	n (%)	n (%)	n (%)
Informed consent	n (%)	n (%)	n (%)
Safety	n (%)	n (%)	n (%)
IP / Treatment Deviation	n (%)	n (%)	n (%)
Other Deviations	n (%)	n (%)	n (%)
Major Deviation	n (%)	n (%)	n (%)
Informed consent	n (%)	n (%)	n (%)
...	n (%)	n (%)	n (%)
Minor Deviation	n (%)	n (%)	n (%)
Informed consent	n (%)	n (%)	n (%)
...	n (%)	n (%)	n (%)

Note: IP = investigational product

path\t\_program.sas date time

**Table 14.1.4.1**  
**Demographic and Baseline Characteristics**  
**Safety Population**

	AD (N= )	bvFTD (N= )	All Subjects (N= )
Age at Informed Consent to Prior Study (years)			
n	n	n	n
Mean (SD)	xx.x (xx.xx)	xx.x (xx.xx)	xx.x (xx.xx)
Median	xx.x	xx.x	xx.x
Min, Max	xx, xx	xx, xx	xx, xx
< 75 years	n (%)	n (%)	n (%)
≥ 75 years	n (%)	n (%)	n (%)
Gender			
Male	n (%)	n (%)	n (%)
Female	n (%)	n (%)	n (%)
Ethnicity			
Hispanic or Latino	n (%)	n (%)	n (%)
Not Hispanic or Latino	n (%)	n (%)	n (%)
Race			
American Indian or Alaska Native	n (%)	n (%)	n (%)
Asian	n (%)	n (%)	n (%)
Black or African American	n (%)	n (%)	n (%)
Native Hawaiian or Other Pacific Islander	n (%)	n (%)	n (%)
White	n (%)	n (%)	n (%)
Other	n (%)	n (%)	n (%)
Multiple Races Checked	n (%)	n (%)	n (%)
Geographic Region			
The Americas	n (%)	n (%)	n (%)
Europe	n (%)	n (%)	n (%)
Rest of World	n (%)	n (%)	n (%)

path\t\_program.sas date time

Table continues on next page.

**Table 14.1.4.1  
Demographic and Baseline Characteristics  
Safety Population**

	AD (N= )	bvFTD (N= )	All Subjects (N= )
Height (cm)			
n	n	n	n
Mean (SD)	xx.x (xx.xx)	xx.x (xx.xx)	xx.x (xx.xx)
Median	xx.x	xx.x	xx.x
Min, Max	xx, xx	xx, xx	xx, xx
Weight (kg)			
n	n	n	n
Mean (SD)	xx.x (xx.xx)	xx.x (xx.xx)	xx.x (xx.xx)
Median	xx.x	xx.x	xx.x
Min, Max	xx, xx	xx, xx	xx, xx
BMI (kg/m  )			
n	n	n	n
Mean (SD)	xx.x (xx.xx)	xx.x (xx.xx)	xx.x (xx.xx)
Median	xx.x	xx.x	xx.x
Min, Max	xx, xx	xx, xx	xx, xx
Subject's Living Accommodation			
Own Home (owner occupied or rented)	n (%)	n (%)	n (%)
Intermediate Forms of Accommodation (not dementia-specific)	n (%)	n (%)	n (%)
Dementia-specific Residential Accommodation	n (%)	n (%)	n (%)
Long-term Institutional Care	n (%)	n (%)	n (%)
Other	n (%)	n (%)	n (%)
Not Available	n (%)	n (%)	n (%)
Who Does the Subject Live With?			
Alone	n (%)	n (%)	n (%)
Spouse	n (%)	n (%)	n (%)
Sibling	n (%)	n (%)	n (%)
Child	n (%)	n (%)	n (%)
Other	n (%)	n (%)	n (%)
Not Applicable	n (%)	n (%)	n (%)
Not Available	n (%)	n (%)	n (%)

path\t\_program.sas date time

*Programming Note: Repeat table for Table 14.1.4.2 Demographic and Baseline Characteristics – Non-AChEI/Memantine Users (Safety Population)*

**Table 14.1.5.1  
Medical History  
Safety Population**

MedDRA System Organ Class High Level Term Preferred Term	AD (N= )	bvFTD (N= )	All Subjects (N= )
SOC1	n (%)	n (%)	n (%)
High Level Term 1	n (%)	n (%)	n (%)
Preferred Term 1	n (%)	n (%)	n (%)
Preferred Term 2	n (%)	n (%)	n (%)
Etc...	n (%)	n (%)	n (%)
High Level Term 2	n (%)	n (%)	n (%)
SOC1	n (%)	n (%)	n (%)
etc.	n (%)	n (%)	n (%)

path\t\_program.sas date time

*Programmer note: Sort table based on SOC order alphabetically*

*Programming Note: Repeat table for Table 14.1.5.2 Medical History – Non-AChEI/Memantine Users (Safety Population)*

**Table 14.1.6.1.1**  
**Concomitant Medications Ongoing On Day 1 of Dosing (Pre-existing Medications)**  
**Safety Population**

ATC Class (Level 1) / ATC Class (Level 3)/ Generic Drug Name	AD (N= )	bvFTD (N= )	All Subjects (N= )
Subjects Receiving Concomitant  Medications	n (%)	n (%)	n (%)
ATC Class (Level 1) 1	n (%)	n (%)	n (%)
ATC Class (Level 3) 1	n (%)	n (%)	n (%)
Generic Drug Name 1	n (%)	n (%)	n (%)
Generic Drug Name 2	n (%)	n (%)	n (%)
.			
.			
ATC Class (Level 3) 2	n (%)	n (%)	n (%)
Generic Drug Name 1	n (%)	n (%)	n (%)
Generic Drug Name 2	n (%)	n (%)	n (%)
.			
.			
ATC Class (Level 1) 2	n (%)	n (%)	n (%)
ATC Class (Level 3) 1	n (%)	n (%)	n (%)
Generic Drug Name 1	n (%)	n (%)	n (%)
Generic Drug Name 2	n (%)	n (%)	n (%)
.			
.			

 Pre-existing concomitant medications are those medications that were ongoing on Day 1 of dosing.

Note: At each level of summation (overall, ATC classes, generic drug name), subjects reporting more than one medication are counted only once. Each summary is ordered alphabetically by ATC class and generic drug name within each ATC class.

path\t\_program.sas date time

*Programming Note: Repeat table for the tables listed below*

*Table 14.1.6.1.2 Concomitant Medications Ongoing On Day 1 of Dosing (Pre-existing Medications) – Non-AChEI/Memantine Users (Safety Population)*

*Table 14.1.6.2.1 Concomitant Medications that Started On or After Day 1 of Dosing (Study-emergent Medications) (Safety Population)*

*Table 14.1.6.2.2 Concomitant Medications that Started On or After Day 1 of Dosing (Study-emergent Medications) – Non-AChEI/Memantine Users (Safety Population)*

*Table 14.1.6.3.1 Concomitant Medications (Pre-existing and Study-emergent Medications) (Safety Population)*

*Table 14.1.6.3.2 Concomitant Medications (Pre-existing and Study-emergent Medications) – Non-AChEI/Memantine Users (Safety Population)*

**Table 14.2.1.1**  
**MMSE**  
**Safety Population**

Time Point	AD (N= )
Baseline 	
n	n
Mean (SD)	xx.x (xx.xx)
Median	xx.x
Min, Max	xx, xx
Week 26	
n	n
Mean (SD)	xx.x (xx.xx)
Median	xx.x
Min, Max	xx, xx
Change from Baseline to Week 26	
n	n
Mean (SD)	xx.x (xx.xx)
Median	xx.x
Min, Max	xx, xx
.	
.	
.	

 Baseline is defined as the last non-missing value prior to first dose of study drug in 020.

path\t\_program.sas date time

**Table 14.2.1.2**  
**MMSE Annualized LS Means**  
**Safety Population**

Time Point	AD (N= )
Baseline 	
n	n
Mean (SD)	xx.x (xx.xx)
Median	xx.x
Min, Max	xx, xx
52 Weeks	
LS Mean 	xx.x
95% CI 	(xx, xx)
104 Weeks	
LS Mean 	xx.x
95% CI 	(xx, xx)
.	
.	
.	

 Baseline is defined as the last non-missing value prior to first dose of study drug in the prior study.

 LS means and 95% CIs are from a restricted maximum likelihood based repeated measures linear mixed model with fixed effects for AChEI/Memantine use as randomized in the prior study (Yes and No), time since baseline in the prior study (continuous), AChEI/Memantine use as randomized in the prior study by time interaction and the prior study baseline MMSE, prior study (015 and 005) and region (The Americas and RoW). In addition, the baseline MMSE was included as a covariate. An unstructured covariance model was used.

**Table 14.2.2**  
**RUD Lite**  
**Safety Population: Subjects with at Least One Post-Baseline RUD Lite Questionnaire**

RUD Lite Items	Time Point	AD (N= )	bvFTD (N= )	All Subjects (N= )
Caregiver Time Spent on Toilet visit, etc. in Last 30 Days	Baseline 			
	n	n	n	n
	Mean (SD)	xx.x (xx.xx)	xx.x (xx.xx)	xx.x (xx.xx)
	Median	xx.x	xx.x	xx.x
	Min, Max	xx, xx	xx, xx	xx, xx
	Week 26			
	n	n	n	n
	Mean (SD)	xx.x (xx.xx)	xx.x (xx.xx)	xx.x (xx.xx)
	Median	xx.x	xx.x	xx.x
	Min, Max	xx, xx	xx, xx	xx, xx
	Change from Baseline to Week 26			
	n	n	n	n
	Mean (SD)	xx.x (xx.xx)	xx.x (xx.xx)	xx.x (xx.xx)
	Median	xx.x	xx.x	xx.x
	Min, Max	xx, xx	xx, xx	xx, xx
	...			
Caregiver Time Spent on Shopping, etc.in Last 30 Days				
...				
Caregiver Time Spent on Supervising in Last 30 Days				
...				
...				

 Baseline is defined as the last non-missing value prior to first dose of study drug.

path\t\_program.sas date time

Table continues on next page.

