If the reason for discontinuation of study drug is an AE, the principal event(s) associated with discontinuation must be specified and recorded. In this case, reasonable effort must be made to clearly document the outcome. If the reason for premature discontinuation is an SAE, this must be documented and an SAE form must be completed (also see Sections 7.1.4 and 7.1.5).

For subjects who withdraw from the study for reasons other than death, or subject or caregiver consent withdrawn (or refusal to continue participation), an early termination visit should be scheduled as soon as possible after the last dose of study drug and identified end of treatment evaluations performed. For subjects who withdraw consent or when a caregiver withdraws consent without available alternate caregiver, the investigator should request that the subject have any clinically indicated safety assessments performed and the reason for withdrawal of consent given.

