8.2 Resource Utilization in Dementia Questionnaire (RUD Lite)

The RUD was developed as a comprehensive instrument to measure resource use by patients in a clinical trial setting, which in a further step can be calculated into costs (Wimo *et al.*, 1998; Wimo *et al.*, 2003; Jonsson, 2007). The RUD Lite is a shorter version of the RUD (Wimo and Winblad, 2003). The RUD and RUD Lite assess both formal and informal resource use, making it possible to calculate costs from a societal perspective. The RUD is administered as an interview with the caregiver. The validity and reliability of the RUD instrument has been investigated both in residential care and community care settings by comparing responses to the RUD questions with actual observations of care-giving time (Jonsson, 2007; Wimo and Nordberg, 2007).

The following dimensions are captured on the subjects' part: accommodation/long term care, respite care, hospital care, social service, and home nursing care. In addition, the following aspects are covered from the caregiver perspective: caregiving time for the subject and work status.

The RUD Lite will be performed at Baseline (if not available from within the prior 42 days) and approximately every 6 months thereafter (or upon early termination).

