9.3 Statistical Analysis

9.3.1 Analysis Populations

The Safety Population will include all subjects who take at least one dose of study drug. Subjects dispensed study medication who subsequently are lost to follow up without any contact are not included in the Safety Population but will be included in the study disposition tabulation and listings. With the exception of study disposition, all tables and listings will be generated on the basis of the Safety Population.

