9.3.3 Health Economic Analysis

A summary of the planned analyses is provided below; a detailed description of the planned analyses, as well as intended sensitivity analyses, will be provided in the SAP.

In order to investigate the pharmacoeconomic impact of LMTM, two approaches will be used:

- a cost consequence analysis (CCA), and
- a cost utility analysis (CUA).

With a cost consequence analysis, a broad set of relevant outcomes (here the primary and secondary outcomes) can be tabulated and discussed in relation to costs (Mauskopf *et al.*, 1998). Costs and outcomes are presented separately.

In the cost utility analysis, the incremental cost effectiveness ratio (ICER) is analyzed. As an outcome, the gained quality adjusted life years (QALY) derived from the EQ5D instrument will be used.

Both pharmacoeconomic approaches mentioned above include a risk of getting non-significant effects regarding costs, as clinical trials evaluating efficacy are typically

underpowered with respect to pharmacoeconomic results and long-term effects cannot be assessed due to time constraints in the clinical trials. Therefore, a modeling approach will complement the analysis.

9.3.3.1 *Resource Use*

The Resource Utilization in Dementia instrument (RUD) is a comprehensive and validated instrument collecting data on resource use in trials, with the aim to calculate costs from a societal viewpoint. The RUD Lite questionnaire, a short version of RUD mainly discarding the resource use by the caregivers, is employed in this study. All subjects for whom RUD Lite data was collected for at least one time point will be included in the summaries.

Together with costs of institutional care, the value of informal care is the heaviest cost driver in dementia care. Three components of caregiver time will be included in the analysis:

- time spent on toilet visits, eating, dressing, grooming, walking and bathing;
- time spent on shopping, food preparation, housekeeping, laundry, transportation, taking medication and managing financial matters; and
- time spent on supervising the subject.

Each component of caregiver time will be calculated as the hours of care on a typical day multiplied by days spent on providing these services. The caregiver time will be summarized for each treatment group by visit and with AChEI and/or memantine status at randomization, severity, and geographic region.

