9.6.6 *Health Economics and Quality of Life Measure*

The individual items and overall scores for the RUD-Lite and EQ-5D-5L will be summarized descriptively by visit. Results will be listed by subject. A summary of the planned analyses is provided in Section 9.3.3; a detailed description of the planned analyses, as well as intended sensitivity analyses, will be provided in the SAP.

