## **4. GENERAL ANALYSIS CONSIDERATIONS**

The Safety population will include all subjects who take at least one dose of study drug. All analyses described in this SAP will be based on the Safety Population. All subjects entering the study, even if not known to have taken a dose, will be accounted for in a listing.

The statistical analyses will be reported using summary tables, figures, and data listings. Continuous variables will be summarized with means, standard deviations, medians, minimums, and maximums. Categorical variables will be summarized by counts and by percentage of subjects in corresponding categories.

For purposes of calculations of change from baseline, Baseline (Visit 1) for the open-label study will be used. Depending on the parameter, the data may have been acquired during the double-blind study of prior participation.

Summary tables will present results by diagnosis (AD or bvFTD) and an “All Subjects” column.

Individual subject data obtained from the CRFs (including mapped data), central clinical laboratory (local laboratory results are entered on the CRFs), and any derived data will be presented by subject in data listings. Listings will include relative study day, where negative values will indicate visits prior to first dose of study drug in 020, and any data collected after discontinuation of study drug will be flagged as follow-up. All data captured on the CRF, including specific descriptions of ‘other’ and comments fields, will be included on the listings. Listings will be sorted by subject number.

All analyses and tabulations will be performed using SAS® Version 9.4 or higher. Tables, listings, and figures will be presented in RTF format. Upon completion, all SAS® programs will be validated by an independent programmer. In addition, all program output will undergo a senior level statistical review. The validation process will be used to confirm that statistically valid methods have been implemented and that all data manipulations and calculations are accurate. Checks will be made to ensure accuracy, consistency with this plan, consistency within tables, and consistency between tables and corresponding data listings. Upon completion of validation and quality review procedures, all documentation will be collected and filed by the project statistician or designee.

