**Table 14.2.3**  
**EQ-5D-5L**  
**Safety Population: Subjects with at Least One Post-Baseline EQ-5D-5L Questionnaire**

	Time Point	AD (N= )	bvFTD (N= )	All Subjects (N= )
Mobility	Baseline 	n=	n=	n=
	I have no problems in walking about	xx (xx.x%)	xx (xx.x%)	xx (xx.x%)
	I have slight problems in walking about	xx (xx.x%)	xx (xx.x%)	xx (xx.x%)
	I have moderate problems in walking about	xx (xx.x%)	xx (xx.x%)	xx (xx.x%)
	I have severe problems in walking about	xx (xx.x%)	xx (xx.x%)	xx (xx.x%)
	I am unable to walk about	xx (xx.x%)	xx (xx.x%)	xx (xx.x%)
	Week 26	n=	n=	n=
	I have no problems in walking about	xx (xx.x%)	xx (xx.x%)	xx (xx.x%)
	I have slight problems in walking about	xx (xx.x%)	xx (xx.x%)	xx (xx.x%)
	...	xx (xx.x%)	xx (xx.x%)	xx (xx.x%)
Self-care	Baseline 	n=	n=	n=
	I have no problems washing or dressing myself	xx (xx.x%)	xx (xx.x%)	xx (xx.x%)
	I have slight problems washing or dressing myself	xx (xx.x%)	xx (xx.x%)	xx (xx.x%)
	...	xx (xx.x%)	xx (xx.x%)	xx (xx.x%)
	Week 26			
	...			
	...			

 Baseline is defined as the last non-missing value prior to first dose of study drug.

Note: Following the 24-Aug-2015 CRF migration, the original EQ-5D-5L eCRF was inactivated and the EQ-5D-5L Patient Rated and EQ-5D-5L Caregiver Rated eCRFs were activated. For the purposes of this summary, data obtained from the original EQ-5D-5L eCRF prior to the 24-Aug-2015 CRF migration and data obtained from the EQ-5D-5L Patient Rated eCRF after the 24-Aug-2015 CRF migration are used.

path\t\_program.sas date time

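### SAP Table 14.2.2 limits the RUD Lite summary to subjects with a post-Baseline questionnaire, against Protocol 9.3.3.1; Table 14.2.3 puts the same unexplained limit on EQ-5D-5L

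*SAP*

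**What the plan says.** **RUD Lite.** Protocol 9.3.3.1 sets the inclusion rule: "All subjects for whom RUD Lite data was collected for at least one time point will be included in the summaries". In SAP Appendix F and in the Appendix G shell, Table 14.2.2 has a narrower population: "Safety Population: Subjects with at Least One Post-Baseline RUD Lite Questionnaire". SAP 8.3, which describes the RUD Lite summaries, mentions no restriction.

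**EQ-5D-5L.** SAP Table 14.2.3 is built on "Safety Population: Subjects with at Least One Post-Baseline EQ-5D-5L Questionnaire". SAP 8.2 is likewise silent. Protocol 9.6.6 asks only for by-visit description, with no subset: "The individual items and overall scores for the RUD-Lite and EQ-5D-5L will be summarized descriptively by visit".

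**General rule.** Protocol 9.3.1, repeated in SAP 5.1: "With the exception of study disposition, all tables and listings will be generated on the basis of the Safety Population". SAP 4: "All analyses described in this SAP will be based on the Safety Population".

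**Timing.** Protocol 8.2 places the RUD Lite at Baseline (unless available from the prior 42 days) and "approximately every 6 months thereafter (or upon early termination"). Protocol 8.3 gives EQ-5D-5L the same follow-up schedule. The first scheduled follow-up questionnaire is therefore at Week 26.

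**Early leavers.** Under Protocol 5.3, for subjects who withdraw "for reasons other than death, or subject or caregiver consent withdrawn (or refusal to continue participation), an early termination visit should be scheduled". Appendix A of the protocol includes both questionnaires at that visit.

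**Changes from the protocol.** SAP 9 lists none and defers any to the study report.

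**The concern.** For RUD Lite the two documents give opposite instructions for the same subject, and a programmer working from the shells will follow the SAP. The restriction appears only in table titles, with no reason given, so a reader cannot tell whether a change was meant.

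What is at stake is the description of the treated population. With the restriction, the column N and every Baseline row describe subjects who were interviewed again, and the tables do not show how many treated subjects have a Baseline questionnaire and nothing after it. That group is not a random subset, because it is formed largely by death, withdrawn consent and loss to follow-up.

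**Working it through.** There is no planned figure to reproduce: Protocol 9.2 gives no sample size calculation, and no document states how many subjects would lack a follow-up questionnaire. The check compares texts, followed by arithmetic for scale only.

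**1. Same subject, two rules.**

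| Subject's data | Protocol rule | SAP table title |
|---|---|---|
| RUD Lite at Baseline only | In (9.3.3.1) | Out (14.2.2) |
| RUD Lite at Baseline and later | In | In |
| EQ-5D-5L at Baseline only | In, by the Safety Population rule (9.3.1) and the unrestricted by-visit summary (9.6.6) | Out (14.2.3) |
| EQ-5D-5L at Baseline and later | In | In |

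The first row contradicts an explicit rule. The third departs from a general one.

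**2. Who has Baseline only.** Take subjects who leave before the Week 26 visit.
- Death: no early termination visit, so Baseline only.
- Consent withdrawn by subject or caregiver, or refusal to continue: Protocol 5.3 exempts them from the visit and has the investigator ask only for clinically indicated safety assessments, so usually Baseline only.
- Lost to follow-up: not exempt, but in practice not seen, so usually Baseline only.
- Adverse events and most other reasons: an early termination visit with both questionnaires is due. SAP 4.4 and Appendix A put early termination visits into the visit windows, so these subjects count as having a post-Baseline questionnaire and stay in.

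**3. Which rows change.** SAP 4.1 bases by-visit percentages on available data. A Baseline-only subject cannot contribute to Week 26, to later visits or to any change row under either rule. Only the column N and the Baseline rows differ. In an invented data set of 1200 subjects, 102 had no follow-up and were given higher Baseline values by construction. The Baseline mean was 59.63 with everyone and 58.14 with the 1098 followed up. Week 26 (n = 1098, mean 63.25) and mean change (5.11) were identical under both rules.

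**4. Scale, on assumed inputs.** Let f be the share with Baseline only. The documents do not give it; 2% to 15% is assumed. Protocol 4.2 projects enrolment N of 1050 to 1400.

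Subjects removed = N × f:
- N = 1050: 1050 × 0.02 = 21; 1050 × 0.15 = 157.5, about 158.
- N = 1400: 1400 × 0.02 = 28; 1400 × 0.15 = 210.

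Baseline mean with everyone minus Baseline mean of those kept = f × d, where d is the mean of those excluded minus the mean of those kept. With d assumed at 0.25 to 1.0 SD in absolute size:
- smallest: 0.02 × 0.25 = 0.005 SD;
- largest: 0.15 × 1.0 = 0.15 SD.

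The sign of d is not known.

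**The case against.** The case for leaving the tables alone has several parts.

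- **The restriction is an ordinary convention.** Protocol 9.6.2 itself limits laboratory Baseline values to subjects with a later value, and both SAP titles describe a subset of the Safety Population. For EQ-5D-5L this has force: no specific rule is broken. For RUD Lite it does not, because the protocol wrote the contrary rule. The laboratory text also shows that the protocol states such a limit where it wants one.
- **The protocol's rule belongs to the health economics, which SAP 8.3 sends to a separate plan.** Only unit costs, modelling and sensitivity analyses go there. The descriptive items of Protocol 9.3.3.1 (caregiver time, work status, hospital and nursing use, accommodation) are what SAP 8.3 keeps and Table 14.2.2 shows.
- **Changes may be declared in the study report.** Protocol 9 allows this, so silence in SAP 9 is not itself a breach. It still leaves the intent unclear.
- **Much of the information is elsewhere.** Baseline living accommodation is in the Table 14.1.4.1 shell and discontinuations by reason and period are in Table 14.1.2.1, both on the Safety Population. Listings 16.2.6.1 and 16.2.6.2.1 to 16.2.6.2.3 keep every subject's questionnaires. This stands and limits the harm. Subtracting the table N from the Safety Population N is not a full substitute, because it mixes Baseline-only subjects with those who have no questionnaire at all.
- **Some withdrawals may have an early termination questionnaire.** The Synopsis, Protocol 4.4 and the Table 4-1 footnotes ask for that visit after premature discontinuation without the consent exception. This also stands, hence usually rather than always in the check.

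**Conclusion.** The point holds. Table 14.2.2, programmed as titled, breaks an explicit protocol rule. Table 14.2.3 departs from the Safety Population rule and from the unrestricted summary of Protocol 9.6.6. The effect is confined to the column N and the Baseline rows of two descriptive tables. Its size is unknown; the 21 to 210 subjects and the 0.005 to 0.15 SD rest wholly on the assumed inputs.

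A reader might infer more, and the documents do not support it:

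- *That both tables break the any-time-point rule.* That rule names RUD Lite only.
- *That follow-up or change results are distorted by the restriction.* Those rows are the same under either population.
- *That Baseline burden is understated.* Heavier Baseline burden among early leavers is plausible, but nothing in the documents shows it.
- *That subjects are removed for poor tolerability.* Those leaving for adverse events should have an early termination questionnaire.
- *That the 60 to 80% completion figure gives the loss.* It is the completion rate assumed for the double-blind studies, used to project enrolment: 1050 / 0.60 = 1400 / 0.80 = 1750. It says nothing about retention in an extension that admits only completers.

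**What to change.** - Set the Table 14.2.2 population to Safety Population subjects with RUD Lite data at one or more time points, in Appendices F and G, and say so in SAP 8.3.
- Do the same for EQ-5D-5L in Table 14.2.3 and SAP 8.2.
- Show n at each visit and keep change rows on subjects with both values.
- Add one row to each table counting subjects with a Baseline questionnaire only.
- If the restriction is intended, state and justify it in SAP 9 as a change from the protocol.

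The cost is two titles, a population flag and one count row per table. No new data are needed. A breakdown of Baseline-only subjects by reason for leaving, with their item values, would be a new table block and is not needed to resolve this point.
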